Hypothesis: Participants will self-administer less alcohol when using the experimental app with feedback.

Secondary Aim: Test increased perceived impairment as a partial mediator of the effects in the prior Aims.

Hypotheses: Participants using the experimental app will report higher perceived impairment, which will mediate relations between app use and lower alcohol consumption in the lab and in the 4-week post period.

Exploratory Aim 1: Test study condition during the lab sessions, amount of alcohol self-administered (operationalized as estimated peak BAC and number of drinks self-administered in separate models) in the group alcohol drinking session and during the field period in the intervention and non-intervention periods as predictors of self-reported alcohol consumption (e.g., drinks per drinking day) and alcohol-related problems self-reported at 6- and 12-months post-session on web-based surveys.

Exploratory Aim 2: Test BACTrack Skyn readings taken during each alcohol administration session as predictors of successive breath alcohol readings taken following alcohol administration/self-administration periods in the alcohol drinking sessions and to predict number of drinks self-administered during the group drinking session.

[figure not shown]
Exploratory Aim 3: Predict scores on self-reported expected involvement in risky behaviors post-alcohol administration based on performance on the app-based cued go/no-go task following a .06% fixed alcohol dose in each alcohol drinking session.

6. Research Plan

Overview

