
Follow-up appointment:

After 4 weeks, participants will come to our office for an updated TLFB and give usability and acceptability ratings for the CGNG experimental feedback app based on the 4-week field period. Staff will extract data from the phones, participants will be paid, and clinical referrals will be provided when appropriate. Participants who participate entirely remotely will complete their follow-up appointment via Password-Protected UF Zoom. Participants will receive \$30 for attending this appointment. They will receive all other earned compensation at this time via a prepaid debit card.

Six- & 12-month follow ups: At six and twelve-months post completion of the study, participants will be contacted via electronic mail and will be asked to complete a survey comprised of

previously approved measures and items regarding use of alcohol reduction smartphone apps and other means of alcohol use reduction. The survey will be completed through the secure website www.REDCap.com. Payment for completion of each survey will be \$25.

Assessments:

Web/phone screener:

Demographic information: This questionnaire assesses basic demographic information, including age, sex, weight, and whether they are a Foreign National or not.

Frequency and quantity of alcohol consumption: Three multiple choice items will be included, which will assess number of drinking days; number of heavy drinking days (5 or more for men, 4 or more for women) and peak number of drinks in a 24-hour period in the past 30 days.

Liking for different alcoholic beverages: An item will be included concerning participants' liking of beer, wine, vodka (straight or in mixer) and rum (straight or in mixer).

General questions regarding other inclusion criteria: Two questions will list several inclusion criteria and ask participants whether or not all of the listed criteria pertain to them. This will provide information regarding inclusion and exclusion to study staff while not requiring participants to provide specific information along these lines as part of the preliminary screen.

In-Person Screening Appointment:

Vital signs (i.e., blood pressure and pulse readings), *height and weight*.

Withdrawal: The *Clinical Institute Withdrawal Assessment for Alcohol (Revised) (CIWA-AR)*²⁹ will be used to assess withdrawal symptoms. The CIWA is a reliable 10-item instrument designed to assess severity of current withdrawal syndrome.

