Impaired control: The *Impaired Control Scale*³³ (*ICS*) consists of three parts including 5 items concerning actual attempts at limiting alcohol consumption (Part 1); 10 items assessing the frequency of past failures at controlling drinking (Part 2) and 10 items assessing beliefs regarding future ability to control drinking (Part 3). Parts 1 and 2 will be administered in this study. The ICS is reliable and has been validated in clinical and community samples. Items are rated on a 0 to 4 scale and summed with higher scores indicating greater difficulty in controlling consumption.

The *Protective Factors Questionnaire* measures frequency of alcohol-related protective strategy use on a 7-point scale. This measure has been used with young adult samples in several studies.

Facets of impulsivity: Impulsivity and risky decision making will be measured using the *UPPS Impulsive Behavior Scale*: a 59-item measure that assesses five subdimensions of impulsivity (premeditation, positive urgency, negative urgency, sensation seeking and perseverance). A *cued go/no-go task*⁶⁰ will be administered during the in-person screening appointment. This is a

8-10 minute computerized task which assesses the ability to inhibit a prepotent response. Subjects are instructed to press a key or inhibit pressing a key based on the colors of the shapes presented. The orientation of the shape (horizontal or vertical) before the color appears signals imperfectly the likelihood that the subsequent stimulus will be “go” or “no-go.” Participants receive feedback regarding their accuracy and speed of response.

In-Person Screening Appointment and at Preliminary Appointment Day of the Sessions:

Self-reported alcohol consumption and smoking: The *Timeline Followback Interview* (TLFB) will be administered at the in-person screening and updated at the preliminary appointment. Participants will be given a blank calendar including memory prompts (e.g., holidays), which covers the designated time interval (the prior 30 days at initial screening) and asked to reconstruct their drinking behavior and smoking over that interval. The TLFB has good test-retest reliability and good validity for verifiable events.

Marijuana use: Participants will be asked on how many days they have used any form or marijuana. Participants will be asked to report on the prior 30 days at the in-person screening appointment and since the in-person screening appointment at the appointment on the day of the session.

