Subjective effects of alcohol: The *Biphasic Alcohol Effects Scale*, a 14-item self-report, unipolar adjective rating scale, will be used to measure the stimulant and sedative effects of alcohol.

Perceived impairment: Participants will also rate their perceived level of impairment with three items on 1-10 scales, used by Brumback et al⁶⁶: 1. “how impaired do you think you are at present?”, 2. “how unsafe do you think it would be to drive an automobile at present?”, and 3. “if I were at work now, others might think I was intoxicated or behaving unusually” with 10-point rating scales for each, anchored at 1 for “not at all” and 10 for “extremely”. The use of these items will allow for analyses to address the possibility that misperceived impairment partially mediates an association between self-reported impaired control and ad libitum alcohol consumption.

“Real Time” Impaired Control Questions: We will ask a series of questions pertaining to impaired control that are based on some items in the Alcohol Craving Questionnaire⁶⁷. The goal is to get a sense of participants’ perceived impaired control at that time if they could drink alcohol without the limitations on drinking in place due to the study: “If I had access to alcohol right now, I would not be able to stop using it;” “I would not be able to control how much alcohol I drank if I had some here now;” “I could not stop myself from drinking if I had some alcohol here.” Items are rated on 7-point scales anchored by “strongly disagree” and “strongly agree.”

Liking for alcohol: An item from *The Drug Effects Questionnaire*⁶⁴ (DEQ) will be used to assess the extent to which participants like the effects of alcohol they are experiencing at the time, rated on a 100-mm line (from “not at all” to “very much”). The DEQ has been utilized in previous alcohol studies⁶⁵.

Craving: Craving be assessed with a *single item assessed using a 100-point visual analog scale*. Participants will be asked to report the extent to which they “want alcohol”

Six and Twelve Month Follow-Up Survey:

Student status: Participants will be asked to report whether or not they are students currently and if so, they will be asked about various aspects of their student status, including full-time versus part-time status, year in school, type of residence and fraternity/sorority membership.

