Psychiatric symptoms/conditions: The 42-item *Depression Anxiety Stress Scale (DASS*⁸⁵) will be administered. This measure assesses several negative emotional states, including depression, anxiety and stress to which participants indicate their agreement on a 4-point scale.

Family history of problem drinking: Family history is measured with a subscale taken from the *Addiction Severity Index*⁵⁷. Participants are asked to indicate whether or not four classes of relatives on both their mother’s and father’s side ever “had a significant problem with alcohol or drugs, one that either lead to treatment or should have led to treatment.”

Alcohol-related problems: Participants will complete the long version of the *Young Adult Alcohol Consequences Questionnaire (YAACQ)*, which is comprised of 48 consequences that may have occurred within the past three months.

Alcohol expectancies: The *Comprehensive Effects of Alcohol (CEOA)* measure will be used to assess the extent to which participants report experiencing alcohol-related expectancies (e.g., “After a few drinks of alcohol, I would be more likely to feel dizzy”).

Subjective response to alcohol: An adapted version of the *Self-rating of Effects of Alcohol (SRE; Schuckit et al., 1997*⁹²) will be used at intake to assess the number of alcoholic drinks it took for participants to experience a series of subjective effects (e.g., stimulation, arousal) the first time they drank alcohol, in the past three months and during their period of heaviest drinking. Responses to the adapted SRE will be used to assess self-reported *tolerance* as well. A tolerance score is created by subtracting the score for the first five drinking occasions ($\alpha = .83$) from the score for the recent drinking experiences ($\alpha = .86$)⁹³.

Drinking motives: Drinking motives will be assessed using Cooper and colleagues measure of three types of drinking motives (i.e., social, coping and enhancement or the achievement of pleasurable affect from drinking).

Drinking-induced disinhibition: The *Drinking-Induced Disinhibition Scale*⁶³ (DIDS) is a measure comprised of a series of drinking-related experiences to which participants are asked to indicate agreement on a six-point scale. The DIDS assesses four types of disinhibitory experiences resulting from alcohol use (i.e., euphoric/social, dysphoric, sexual and aggressive).

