Impaired control: The *Impaired Control Scale*³³ (ICS) consists of three parts including 5 items concerning actual attempts at limiting alcohol consumption (Part 1); 10 items assessing the frequency of past failures at controlling drinking (Part 2) and 10 items assessing beliefs regarding future ability to control drinking (Part 3). Parts 1 and 2 will be administered in this study. The ICS is reliable and has been validated in clinical and community samples. Items are rated on a 0 to 4 scale and summed with higher scores indicating greater difficulty in controlling consumption.

The *Protective Factors Questionnaire* measures frequency of alcohol-related protective strategy use on a 7-point scale. This measure has been used with young adult samples in several studies.

Facets of impulsivity: Impulsivity and risky decision making will be measured using the *UPPS Impulsive Behavior Scale*: a 59-item measure that assesses five subdimensions of impulsivity (premeditation, positive urgency, negative urgency, sensation seeking and perseverance). A *cued go/no-go task*⁶⁰ will be administered during the in-person screening appointment. This is a 8-10 minute computerized task which assesses the ability to inhibit a prepotent response. Subjects are instructed to press a key or inhibit pressing a key based on the colors of the shapes presented. The orientation of the shape (horizontal or vertical) before the color appears signals imperfectly the likelihood that the subsequent stimulus will be “go” or “no-go.” Participants receive feedback regarding their accuracy and speed of response.

Smartphone app use: Several questions will ask participants about their use of smartphone applications during the past 6-months as a way to moderate or reduce their drinking.

Drinking reduction: Two questions will assess whether participants have taken active (i.e., attending self-help group meetings, beginning psychotherapy, medication use or entering an inpatient facility) steps to change their alcohol and/or other substance use during the past 6-months

Data analyses

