coefficients in calculating indirect effects of IV on DV, operating through a mediator. When the CI does not include 0, an indirect effect is significant at the specified alpha level.

For Exploratory Aim 1, we will test between-subjects study condition during the lab sessions, amount of alcohol self-administered (operationalized as estimated peak BAC and number of drinks self-administered in separate models) in the alcohol drinking session and during the field period in the intervention and non-intervention periods as predictors of self-reported alcohol consumption (e.g., drinks per drinking day) and alcohol-related problems self-reported at 6- and 12-months post-session on the web-based surveys using MLM. Baseline reports of each alcohol-related outcome and participant sex will be entered as covariates. The web-based surveys at baseline, 6- and 12-months post also include measures of several potential covariates that may be entered into these models should they differ significantly across study conditions.

For Exploratory Aim 2, we will use separate MLMs to test BACTrack Skyn readings during each alcohol administration session as predictors of successive breath alcohol readings taken following alcohol administration/self-administration periods in the alcohol drinking sessions and to predict number of drinks self-administered during the group drinking session. Sex and participant weight will be entered into these models as covariates as well.

For Exploratory Aim 3, we will use MLM to predict expected involvement scores on the CARE measure post-alcohol administration based on performance on the app-based cued go/no-go task following the .06% fixed dose as the predictor variable. Baseline expected involvement scores and scores on the other CARE subscales will be held constant in these models. Since the .06% dose will be administered at each session along with cued go/no-go task performance and the CARE, these measures will be entered into the same models as repeated measures. Participant sex and study condition will also be entered as covariates in these models

Sample, power & effect size

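### No instrument listed for the 6- and 12-month survey measures drinking quantity or frequency, although Exploratory Aim 1 takes its consumption outcome from that survey

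*Combined protocol and SAP*

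**What the plan says.** Two places define the outcomes of Exploratory Aim 1, and they agree. Section 5 (Specific Aims) names "self-reported alcohol consumption (e.g., drinks per drinking day) and alcohol-related problems self-reported at 6- and 12-months post-session on web-based surveys". The Data analyses part of section 6 repeats this and gives the method: "self-reported alcohol consumption (e.g., drinks per drinking day) and alcohol-related problems self-reported at 6- and 12-months post-session on the web-based surveys using MLM". The same paragraph calls for a baseline value of each outcome, together with sex, as covariates.

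Two places describe the survey that is to supply these outcomes. The follow-up part of section 6 says that it is sent by e-mail, completed in REDCap, and made up of "previously approved measures and items regarding use of alcohol reduction smartphone apps and other means of alcohol use reduction". The Assessments part then itemises it under the heading "Six and Twelve Month Follow-Up Survey".

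On the TLFB, the Assessments part says: "The *Timeline Followback Interview* (TLFB) will be administered at the in-person screening and updated at the preliminary appointment". The follow-up appointment after the 4-week field period adds one further update. No TLFB is scheduled after that.

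**The concern.** An analysis can use only what the survey asks. The aim needs two things from the 6- and 12-month contacts: a measure of drinking and a measure of problems. The itemised survey appears to contain only the second. These two surveys are the only assessments planned after the 4-week follow-up, and there is no interview alongside them, so no other source at those times would fill the gap. A survey built from the protocol's own list would leave one of the two outcomes of Exploratory Aim 1 without data. That outcome bears directly on the app's purpose, which is to reduce drinking.

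**Working it through.** The plan gives no sample size, power or alpha for Exploratory Aim 1, so there is no figure to reproduce. The check is an inventory of the survey set against the outcomes the aim requires.

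**Step 1. What the aim needs.** Two outcomes (consumption, problems) at two times (6 and 12 months): 2 × 2 = 4 outcome-by-time combinations.

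**Step 2. What the survey lists.** The entries between the survey's heading and the Data analyses heading are:

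| # | Entry | Drinking quantity or frequency? | Problems? |
|---|---|---|---|
| 1 | Student status | no | no |
| 2 | DASS | no | no |
| 3 | Family history of problem drinking | no | no |
| 4 | YAACQ | no | yes |
| 5 | Alcohol expectancies (CEOA) | no | no |
| 6 | Adapted SRE | no | no |
| 7 | Drinking motives | no | no |
| 8 | Drinking-induced disinhibition (DIDS) | no | no |
| 9 | Impaired Control Scale, Parts 1 and 2 | no | no |
| 10 | Protective Factors Questionnaire | no | no |
| 11 | UPPS | no | no |
| 12 | Cued go/no-go text | no | no |
| 13 | Smartphone app use | no | no |
| 14 | Drinking reduction | no | no |

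Result: 0 of 14 for quantity or frequency, 1 of 14 for problems.

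**Step 3. The entries that come closest.**
- The YAACQ is the measure "which is comprised of 48 consequences that may have occurred within the past three months". It counts consequences, not drinks.
- The adapted SRE involves drink counts, but they are the drinks needed to feel given effects. That is sensitivity and tolerance, not consumption.
- The Impaired Control Scale rates attempts and failures to limit drinking on a 0 to 4 scale.
- The app-use entry reads "Several questions will ask participants about their use of smartphone applications during the past 6-months as a way to moderate or reduce their drinking". It concerns apps, not amounts.
- The drinking-reduction entry asks about steps such as self-help groups, therapy, medication or inpatient care.

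**Step 4. Consumption measures elsewhere in the protocol.**
- Web/phone screener: three multiple-choice items on drinking days, heavy drinking days and peak drinks in the past 30 days. They are listed for the screener only.
- Baseline web survey: the one quantity item is a lifetime maximum, under drinking history. That entry is not repeated in the 6- and 12-month list.
- TLFB: screening (prior 30 days), preliminary appointment, 4-week follow-up.
- Morning app report of the prior day's drinks: ends with the 4-week field period.
- EMA surveys: confined to the 10-day EMA scenario.

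None falls at 6 or 12 months.

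**Step 5. Count.** Problems at 6 and 12 months are covered by the YAACQ (2 combinations). Consumption at 6 and 12 months has no listed instrument (4 − 2 = 2 combinations).

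**Step 6. A likely origin.** The follow-up list largely repeats the baseline web survey. It still describes the SRE as given at intake and the go/no-go task as given at the in-person screening. At baseline, drinking is captured by the separate TLFB interview, so that web survey did not need it. Carried forward without the interview, the list no longer covers drinking. This is an inference from the text; the protocol does not say it.

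**The case against.** The strongest reply is that the list may not be exhaustive. The general description, "previously approved measures and items regarding use of alcohol reduction smartphone apps and other means of alcohol use reduction", is open-ended, and the screener's quantity and frequency items are already among the protocol's measures. Both statements of the aim say that consumption is self-reported on these surveys, so the intent to collect it is plain. The list also carries visible leftovers from baseline, which makes it weak evidence of what the fielded form omits. This reply stands to the following extent: a reader might infer that the consumption outcome is certain to be absent from the trial's data, and the documents do not support that. They show only that no listed instrument supplies it. The reply does not remove the gap, because no passage names a consumption measure or a recall window for these surveys, and the model needs both in order to match a baseline value.

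Three further readings are tempting and are not supported.
- That the loss would be irreparable. Surveys go out at each participant's own 6- and 12-month point, so an added item would still capture every survey not yet completed, including 12-month surveys of people already past 6 months.
- That the gap deprives the planned R01 of its long-term drinking data. The protocol links the R01 to the study in general and to the app's effect on self-administration. It never links it to the 6- and 12-month data.
- That only drinks per drinking day would do. The aim offers that metric as an example, so drinking days or heavy drinking days would also count as consumption. The list has no item for those either.

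It is also fair to say that the aim is exploratory and that the study was powered for the primary and secondary aims.

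**Conclusion.** The point holds as an inconsistency between an aim and its data source. If the 6- and 12-month survey is fielded as itemised, the consumption outcome of Exploratory Aim 1 cannot be analysed: 0 of 14 entries measure it, and 2 of 4 outcome-by-time combinations have no instrument. The problems outcome is covered by the YAACQ. The primary and secondary aims and their stated power are untouched. The conclusion rests on one assumption, that the itemised list is what will be fielded. If the form in use already contains a consumption item, what remains is a documentation gap: the item, its recall window and its matching baseline value still have to be stated. Given the exploratory status of the aim and the low cost of the remedy, this should be corrected but does not threaten the trial's main conclusions.

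**What to change.** Add to the 6- and 12-month REDCap survey a self-completed past-30-day drinking measure from which drinks per drinking day can be derived. A daily drinking calendar is one suitable form. It would match the 30-day window of the screening TLFB and would also yield drinking days and heavy drinking days. List it under the survey's heading in Assessments. In the Exploratory Aim 1 analysis paragraph, name the screening TLFB value as its baseline covariate.

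Reusing the three screener items would be shorter and would fit the aim's broad wording, but they do not give drinks per drinking day.

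If no consumption measure is to be collected, remove consumption from Exploratory Aim 1 in both Specific Aims and Data analyses.

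The cost is one added web form of a few minutes and a minor IRB amendment, with no extra visit or staff. The survey becomes slightly longer, and a self-completed web calendar differs in mode from an interview TLFB. The report should note this when follow-up values are adjusted for, or compared with, baseline.
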